11.4. Definition of End of Study

End of Study (EoS) will be upon completion of the follow-up period for the last patient treated in the study. Completion of follow-up for the last patient will occur when the last patient in the study has expired, has been followed for 24 months after enrollment, has been lost to follow-up, or has withdrawn consent, whichever occurs first.

12. TREATMENT

Selinexor (KPT-330) immediate release tablets for oral administration and matching placebo will be supplied in blister packs. Selinexor tablets will be provided in a coated tablet strength of 20 mg.

12.1. Dosing and Administration of Study Treatment

12.1.1. Labeling

Medication labels for each blister pack of selinexor and matching placebo tablets will be in the local language and comply with the legal requirements of each country. They will include storage conditions for the drug and the randomization number but no information about the patient.

12.1.2. Dispensing Directions

The Investigator or responsible site personnel must instruct the patient or caregiver to take the study treatment as per protocol. Study treatment will be dispensed to the patient by authorized site personnel only. Dispensing instruction will be provided in the *Pharmacy Manual*.

12.1.3. Dosing Information

Selinexor tablets should be taken orally with at least 120 mL (4 ounces) of water. Selinexor can be taken with or without food. For additional details on drug formulation, preparation, and administration, please refer to the *Pharmacy Manual* and the selinexor IB.

In order to avoid contact with skin, tablets must be swallowed whole and should not be crushed.

Blinded Study Treatment (Phases 2 and 3):

Selinexor and matching placebo will be administered as fixed blinded oral doses of three 20 mg tablets given twice weekly (eg, Day 1 Monday and Day 3 Wednesday or Day 1 Tuesday and Day 3 Thursday or Day 1 Wednesday and Day 3 Friday) on Weeks 1-6 of each 6-week (42-day) cycle until PD, intolerance, consent withdrawal, or unblinding. Patients with a BSA < 1.2 m² as calculated per [Dubois 1916](#) or [Mosteller 1987](#) will be excluded from the study. Selinexor will be administered as a flat-fixed dose, and not by body weight or BSA.

Open-Label Selinexor:

Patients on open-label selinexor will receive selinexor 60 mg twice-weekly during Weeks 1-6 of each 6-week (42-day) cycle.

The following 4 groups of patients may receive open-label selinexor:

- (a) Patients in the placebo arm who have PD per RECIST v. 1.1 during blinded study treatment who elect to cross over to open-label selinexor

- (b) Patients in the selinexor arm who have PD per RECIST v. 1.1 during blinded study treatment who may derive benefit from continued treatment with selinexor (see Section 7.2.4).
- (c) Patients in the placebo arm who are receiving blinded study treatment at the time of the primary PFS analysis at the end of Phase 3 who elect to continue to cross over to open-label selinexor
- (d) Patients in the selinexor arm who are receiving blinded study treatment at the time of the primary PFS analysis at the end of Phase 3 who elect to continue selinexor but as open-label treatment

C1D1 of treatment with open-label selinexor for all 4 groups of patients listed above must occur within 14 days of the patient's EoBT Visit. For patients in the selinexor arm during blinded study treatment who continue selinexor but as open-label treatment there will be no break in the patient's twice-weekly dosing schedule. These patients must complete the EoBT Visit before their next scheduled selinexor dose to maintain continuity of selinexor dosing from blinded to open-label treatment.

12.1.4. Dosing Instructions for the Study Participants

Study treatment will be provided for twice weekly dosing during Weeks 1-6 for all cycles. Patients will be provided adequate doses to take home to complete dosing until the next scheduled clinic visit. Patients will be asked to bring remaining study medicine, if any, when returning to the clinic for any scheduled or unscheduled visit.

The Investigator should promote compliance by instructing the patient to take the study treatment exactly as prescribed and by stating that compliance is necessary for the patient's safety and the validity of the study. The patient should be instructed to contact the Investigator if he/she is unable for any reason to take the study treatment.

Supportive treatment for the management of known toxicities will be provided as needed.

All dosages prescribed and dispensed to the patient and all dose changes during the study must be recorded on the eCRF. Compliance to study treatment will be recorded by study personnel after discussion with the patient and completion of drug accountability. Medication compliance will be monitored by the Investigator or a delegate and recorded in source documents. The date will be recorded as per the study treatment schedule. The Investigator or designee will account for the number of tablets dispensed against those returned by the patient. Any deviations and missed doses will be recorded in the eCRF and drug accountability logs for verification of explanations for deviations. The Investigator or designee will try to ensure complete compliance with the dosing schedule by providing timely instructions to the patients and re-education when necessary.

12.2. Dose Reduction and Supportive Care Guidelines

12.2.1. Dose Modifications and Dose Delay

For patients who do not tolerate the protocol-specified dosing schedule, dose adjustments are permitted in order to allow the patient to continue the study treatment. The criteria for dose modifications for toxicities considered related to the study treatment, as well as

recommended supportive care, are outlined below and in Section 12.2. All interruptions or changes to study treatment administration must be recorded on the eCRF.

A dose reduction should be considered if the patient missed 2 consecutive doses or 3 nonconsecutive doses in a cycle due to an AE(s). The missed doses may be the result of a combination of AEs during the cycle (eg, Day 1 doses of Weeks 1 and 2 missed due to nausea, Day 1 dose of Week 3 missed due to fatigue). Following a dose reduction, dose re-escalation is allowed only after consultation with the Sponsor Medical Monitor.

Patients who require extended dose interruptions without disease progression (eg, unacceptable toxicities) will remain on study and continue with tumor scans per schedule of assessments as specified in [Table 1](#) and [Table 2](#).

Patients who withdraw from the study for a study-related AE or an abnormal laboratory value must be followed as described in Section 13.1.2. Based on observations from the Phase 1 studies in patients with advanced hematological and solid tumors, selinexor shows a reasonably wide therapeutic range with activities from ~ 10 mg/m² to ≥ 60 mg/m². Based on observations in over 1000 patients treated with selinexor alone or in combination with other agents, fatigue, anorexia and weight loss associated with selinexor are highly variable and patient-specific. Therefore, in order to optimize specific antitumor activity and the patient's tolerability, we will allow for dose or schedule modifications as described in Section 12.2 below and in [Table 9](#) (pre-specified dose/schedule modifications for AEs related to study treatment and supportive care/dose adjustment guidelines, respectively. Patients should also be treated aggressively with supportive care to reduce toxicities. If more than one different type of toxicity occurs concurrently, the most severe grade will determine the modification.

For all \geq Grade 3 hematological or Grade 3 non-hematological AEs that are NOT treatment related, after consultation with the Medical Monitor and at the discretion of the Investigator, dosing may be maintained provided that the patient can continue to take the agent by mouth.

For all Grade 4 non-hematologic toxicities, protocol-specified study treatment (selinexor/placebo) must be suspended and the Sponsor Medical Monitor consulted regarding options for continuation (ie requirements for resuming study treatment or permanent discontinuation).

Table 8: Pre-specified Dose/Schedule Modifications for Adverse Events Related to Selinexor/Placebo Treatment

| Dose Level¹ | Dose/Schedule Modifications of Selinexor/Placebo² | |
|---------------------------------|---|--|
| | Total mg Selinexor/Placebo Per Week | Selinexor/Placebo Dose/Schedule |
| Dose level 0 (starting dose) | 120 mg | 60 mg selinexor/placebo (3 tablets) twice weekly (Day 1, Day 3) |
| Dose level -1 | 100 mg | 100 mg selinexor/placebo on Day 1 OR divided as 60 mg selinexor/placebo on Day 1 and 40 mg selinexor/placebo on Day 3 |
| Dose level -2 | 80 mg | 80 mg selinexor/placebo on Day 1 OR 40 mg selinexor/placebo on Days 1 and 3 |
| Dose level -3 | 60 mg | 60 mg selinexor/placebo on Day 1 OR divided as 40 mg selinexor/placebo on Day 1 and 20 mg selinexor/placebo on Day 3 |
| Dose level -4 | 40 mg | 40 mg selinexor/placebo on Day 1 OR 20 mg selinexor/placebo on Days 1 and 3 |

¹For some AEs, dose interruption rather than reduction is recommended. See [Table 9](#) for specific recommendations.

²All placebo doses will contain 0 mg of selinexor.

Table 9: Supportive Care and Dose Adjustment Guidelines for Selected Adverse Events

| Toxicity and Intensity | Supportive Care and Dose Adjustment Guidelines |
|--|---|
| Fatigue | |
| Grade 1 | 
Maintain dose. Rule out other causes. If found to be anemic and symptomatic, consider transfusing even with hemoglobin >8 g/dL (anemia Grade <3).
 
Patients with significant fatigue after several doses of selinexor may have an antitumor response. Consider an unscheduled assessment of tumor response as part of the patient's evaluation.
 |
| Grade 2 lasting ≤7 days | 
As per NCCN guidelines, consider stimulants such as methylphenidate 5mg QD in the morning only.
 |
| Grade 2 lasting >7 days or Grade ≥3 | 
Rule out other causes. If found to be anemic and symptomatic, consider transfusions for hemoglobin >8 g/dL (Grade <3); transfusions usually indicated for Hb <8 g/dL (Grade ≥3). Interrupt selinexor dosing until resolved to Grade 1 or baseline.
 
For first occurrence, restart selinexor at current dose.
 
For ≥ second occurrence, reduce selinexor by 1 dose level.
 
Patients with significant fatigue after several doses of selinexor may have an antitumor response. Consider an unscheduled assessment of tumor response as part of the patient's evaluation.
 
As per NCCN guidelines, consider stimulants such as methylphenidate 5mg QD in the morning only.
 |
| Anorexia or Weight loss | |
| Grade 1 anorexia | 
Maintain dose. Rule out other causes. Consider nutritional consultation and use nutritional supplements (eg, Ensure®, Boost®).
 
For persistent symptoms, initiate appetite stimulants, such as olanzapine (2.5 to 5 mg PO every morning) or megestrol acetate (400 mg QD), as per NCCN guidelines.
 |
| Grade 1 weight loss Grade 2 anorexia | 
Initiate appetite stimulants, such as olanzapine (2.5 to 5 mg PO every morning) or megestrol acetate (400 mg QD), as per NCCN guidelines.
 |
| Grade 2 weight loss Grade 3 anorexia, or Grade 3 weight loss | 
Interrupt selinexor dosing until improved to Grade 1 or baseline and weight stabilizes. Reduce selinexor by 1 dose level.
 
Rule out other causes. Consider nutritional consultation and use nutritional supplements (eg, Ensure®, Boost®)
 
Initiate appetite stimulants as above,
 |

| Toxicity and Intensity | Supportive Care and Dose Adjustment Guidelines |
|---|---|
| Nausea, Acute | |
| Grade 1 or 2 | 
Maintain dose. Rule out other causes. Use standard additional anti-nausea medications to supplement the protocol-required 5-HT3 antagonists.
 
If persistent, use additional anti-nausea medications to supplement the protocol-required 5-HT3 antagonist(s). Olanzapine 2.5 to 5 mg PO every morning, as per NCCN guidelines, can mitigate nausea and anorexia.
 |
| Grade 3 | 
Rule out other causes. Use additional anti-nausea medications to supplement the protocol-required 5-HT3 antagonist(s). Olanzapine 2.5 to 5 mg PO every morning, as per NCCN guidelines, can mitigate nausea and anorexia.
 
Interrupt selinexor dosing until resolved to Grade ≤ 2 or baseline and reduce selinexor by 1 dose level.
 
Patients with significant nausea/vomiting after several doses of selinexor may have an antitumor response. Consider an unscheduled assessment of tumor response as part of the patient's evaluation.
 |
| Hyponatremia | |
| Grade 1 (sodium levels < Normal to 130 mmol/L) | 
Maintain dose. Rule out other causes including drug (eg, diuretic) effects.
 
Be certain that reported sodium level is corrected for concurrent hyperglycemia (serum glucose > 150 mg/dL).
 
Treat hyponatremia per institutional guidelines including dietary review. Provide supplemental oral and/or intravenous fluids if dehydration is present. Consider addition of salt tablets to patient's diet.
 |
| Grade 3 with sodium levels <130-120 mmol/L without symptoms | 
Rule out other causes including drug (eg, diuretic) effects.
 
Be certain that reported sodium level is corrected for concurrent hyperglycemia (serum glucose > 150 mg/dL).
 
If (corrected) sodium is Grade ≤ 3 and continues to be asymptomatic, then patient may continue current dosing without interruption provided that IV saline and/or salt tablets are provided and patient is followed closely.
 
If Grade 3 is persistent or worsens or does not respond to treatment, interrupt selinexor dosing until resolved to Grade 1 or baseline and reduce selinexor by 1 dose level.
 |
| Grade 3 with sodium levels <130-120 mmol/L with symptoms or Grade 4 (<120 mmol/L) | 
Rule out other causes including drug (eg, diuretic) effects.
 
Be certain that reported sodium level is corrected for concurrent hyperglycemia (serum glucose > 150 mg/dL).
 
Interrupt selinexor dosing until resolved to Grade 1 or baseline and without symptoms. Reduce selinexor by 1 dose level.
 |
| Diarrhea | |
| Grade 1 | 
Maintain dose. Rule out other causes including drug effects. Treat per institutional guidelines with anti-diarrheals, such as loperamide.
 |
| Grade 2 | 
Rule out other causes including drug effects. Treat per institutional guidelines with anti-diarrheals. Interrupt selinexor dosing until resolved to Grade 1 or baseline.
 
For first occurrence, restart selinexor at current dose.
 
For \geq second occurrence, reduce selinexor by 1 dose level.
 |
| Grade 3 or 4 | 
Interrupt selinexor dosing until resolved to Grade 1 or baseline and patient is clinically stable. Reduce selinexor dose by 1 dose level.
 |

| Toxicity and Intensity | Supportive Care and Dose Adjustment Guidelines |
|---|---|
| Thrombocytopenia | |
| Grade 1 or 2 | Maintain dose. Rule out other causes including drug effects. |
| Grade 3 without bleeding | 
Rule out other causes including drug effects.
 
For first occurrence: skip 1 dose and reduce selinexor by 1 dose level.
 
If recurrent, unless contraindicated, initiate treatment with moderate to high doses of thrombopoietin stimulating agents such as romiplostim 5 to 10 µg/kg SC weekly (preferred) or eltrombopag 100 to 150 mg QD.
 
In cases where there is significant disease involvement in the bone marrow or pre-existing compromised marrow function (eg, due to prior marrow-toxic therapy), or if there is thrombocytopenia Grade 2 to 4 at baseline, the Investigator in consultation with the Medical Monitor may decide to continue selinexor dosing without dose reductions and/or interruptions as specified above, provided that platelet counts and bleeding symptoms/signs are closely monitored. Thrombopoietin stimulating agents are recommended.
 |
| Grade 4 without bleeding | 
Rule out other causes including drug effects.
 
Interrupt selinexor until patient recovers to Grade 2 or baseline.
 
Selinexor dosing may be reduced by 1 dose level (it is recommended to have only 1 dose modification per cycle)
 
If recurrent, unless contraindicated, initiate treatment with moderate to high doses of thrombopoietin stimulating agents as above.
 
In cases where there is significant disease involvement in the bone marrow or pre-existing compromised marrow function (eg, due to prior marrow-toxic therapy), the Investigator in consultation with the Medical Monitor may decide to continue selinexor dosing without dose reductions and/or interruptions as specified above, provided that platelet counts and bleeding symptoms/signs are closely monitored.
 |
| Grade ≥ 3 with bleeding | 
Interrupt selinexor dosing and check platelet counts weekly until the bleeding has stopped, patient is clinically stable and the platelets have recovered to Grade 2 or baseline. When resuming selinexor, reduce by 1 dose level.
 
If recurrent, unless contraindicated, initiate treatment with moderate to high doses of thrombopoietin stimulating agents as above.
 |
| Neutropenia | |
| Grade 3 or 4 neutropenia (afebrile) OR Febrile neutropenia | 
Institute colony stimulating factors and prophylactic antibiotics as clinically indicated per institutional guidelines.
 
Interrupt selinexor and check neutrophils at least weekly until recovers to Grade 2 or baseline and without fever (if febrile) and the patient is clinically stable. Reinitiate selinexor therapy and colony stimulating factors per institutional guidelines.
 
If recurrent, continue colony stimulating factors, interrupt selinexor until neutrophil counts improve to Grade ≤ 2 or baseline levels, and reduce dose of selinexor 1 dose level.
 |
| Anemia | |
| Treat per institutional guidelines including blood transfusions and/or erythropoietins. Consider transfusing for symptoms with hemoglobin > 8 g/dL (Grade < 3) or for any Grade 3 (hemoglobin < 8 g/dL). If possible, maintain selinexor dose as long as patient is clinically stable, but if a dose reduction or interruption is desired, consult with the Medical Monitor. | |

| Toxicity and Intensity | Supportive Care and Dose Adjustment Guidelines |
|--|---|
| Tumor lysis syndrome | |
| If TLS risk factors are identified, provide prophylactic IV hydration and regular monitoring of hydration (especially when increasing the dose of selinexor), renal function, urine output, and clinical laboratory measures of interest for TLS (eg, phosphorus, potassium, calcium, LDH, uric acid). Consider administration of hypouricemic agents to reduce the risk of TLS. | |
| Hold selinexor in patient with hyperkalemia (≥ 7.0 mmol/L) and/or symptoms of hyperkalemia, an increase in uric acid, or other changes in biochemical blood parameters suggestive of TLS. Start IV hydration, and consider hypouricemic agent until levels return to normal. Selinexor can be reintroduced at the normal or reduced dose. | |
| Other selinexor-related adverse events | |
| Grade 1 or 2 | Rule out other causes. Maintain dose. Start treatment and/or standard supportive care per institutional guidelines. |
| Grade 3 or 4 | Rule out other causes. Interrupt selinexor until recovers to Grade 2 or baseline and reduce selinexor by 1 dose level. Isolated values of Grade ≥ 3 alkaline phosphatase do NOT require dose interruption. Determination of liver versus bone etiology should be made, and evaluation of gamma-glutamyl transferase, 5'-nucleotidase, or other liver enzymes should be performed. |

IV: intravenous; NCCN: National Comprehensive Cancer Network; QD: once daily; PO: oral; SC: subcutaneous; TLS: tumor lysis syndrome.

^aFor all Grade ≥ 3 hematologic or non-hematologic AEs that are NOT selinexor related, after consultation with the Medical Monitor and at the discretion of the Investigator, selinexor dosing may be maintained.

^bFor all selinexor-related AE's, if the below prescribed dose reductions/interruptions result in a stabilization of ≥ 4 weeks, a re-escalation may be considered after approval from the Medical Monitor.

All dose modifications should be based on the worst preceding toxicity.

Note: When toxicities due to selinexor have returned to baseline levels or the patient has stabilized, the dose of selinexor may be re-escalated in consultation with the Medical Monitor.

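### Section 12.2.1 and Table 9 footnote a give conflicting instructions on whether dosing must stop for a Grade 4 non-hematologic adverse event judged unrelated to study treatment

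*Protocol*

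**What the plan says.** Protocol Section 12.2.1 has two adjacent paragraphs that matter here.

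- The first is a permission. It covers "Grade 3 hematological or Grade 3 non-hematological AEs that are NOT treatment related", with a greater-than-or-equal sign in front of the hematologic grade only. For these events, after Medical Monitor consultation and at the Investigator's discretion, "dosing may be maintained provided that the patient can continue to take the agent by mouth".
- The second is a requirement: "For all Grade 4 non-hematologic toxicities, protocol-specified study treatment (selinexor/placebo) must be suspended and the Sponsor Medical Monitor consulted". The stated subject of the consultation is how, or whether, to continue: "consulted regarding options for continuation (ie requirements for resuming study treatment or permanent discontinuation".

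Table 9, in the same section, carries its own version of the permission in footnote a. It covers events of Grade 3 or higher, hematologic or not, and its non-hematologic limb reads "non-hematologic AEs that are NOT selinexor related". After consultation with the Medical Monitor, "at the discretion of the Investigator, selinexor dosing may be maintained".

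For related events, Table 9 has rows with recovery thresholds. The row for other selinexor-related events at Grade 3 or 4 reads "Interrupt selinexor until recovers to Grade 2 or baseline and reduce selinexor by 1 dose level". The rows for diarrhea at Grade 3 or 4, and for symptomatic Grade 3 or any Grade 4 hyponatremia, follow the same pattern with recovery to Grade 1 or baseline.

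**The concern.** The permission appears twice, in nearly the same form, with different grade limits for non-hematologic events. The narrower version is followed at once by a mandatory rule for the grade it leaves out, and the wider version takes that grade back in. A site reading the body text and a site reading the table footnote could handle the same event differently, and each could point to the protocol in support.

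The events are serious ones. Where the Common Terminology Criteria for Adverse Events (CTCAE) provide no grading for an event, Protocol Section 13.1.3 defines Grade 4 as life-threatening. Whether dosing stops should not turn on which page is consulted. There is also a smaller consequence for reporting: the SAP tabulates interruptions and reductions as part of exposure (Section 3.4.1) and AEs leading to dose modification (Section 5.1.3), so differing site practice would feed into those tables.

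**Working it through.** There is no figure to reproduce; the check is a comparison of texts.

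**Step 1. Put the two permissions for unrelated events side by side.**

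| | Section 12.2.1, body text | Table 9, footnote a |
|---|---|---|
| Hematologic | Grade 3 or higher | Grade 3 or higher |
| Non-hematologic | Grade 3 | Grade 3 or higher |
| Medical Monitor consulted | Yes | Yes |
| Investigator discretion | Yes | Yes |
| Patient must be able to take the drug orally | Yes | Not stated |
| Action | Dosing may be maintained | Dosing may be maintained |

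The two differ in two cells: the non-hematologic grade limit and the oral-intake condition.

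**Step 2. Place an unrelated Grade 4 non-hematologic AE in each.**

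- Section 12.2.1: it is outside the permission, which stops at Grade 3 for this class. The next paragraph applies to every Grade 4 non-hematologic toxicity and says nothing about relatedness. Result: suspend and consult.
- Footnote a: it is inside the permission. Result: consult, after which dosing may be maintained.

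The same event thus falls under a mandatory stop and under a discretionary continuation.

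**Step 3. Look for a tie-breaker.** Section 12.2.4 lists conditions declared to be exceptions to the guidelines: alopecia, electrolyte or analyte abnormalities reversible with standard interventions, and isolated Grade 3 or higher alkaline phosphatase. Unrelated AEs as a class are not listed, so that section does not settle the matter. Nothing in Section 12.2.1 or Table 9 says which prevails over the other.

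**Step 4. Check related Grade 4 events.** Both texts stop dosing. Section 12.2.1 requires consultation on resumption or discontinuation; the Table 9 rows give a recovery threshold and a one-level reduction. A site can suspend, consult, and then apply the row, so both can be obeyed together. What is missing is a sentence saying how the consultation and the row relate. This is a gap in wording and not a conflict.

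**The case against.** The best counter-argument is that the word toxicities in the Grade 4 sentence means related events only. Section 12.2.1 opens by introducing its criteria as being for toxicities considered related, and the paragraph on unrelated events speaks of AEs instead. On that reading the Grade 4 sentence governs related events, footnote a governs unrelated ones, and the contradiction goes away. This is arguable but strained. The sentence says all, and the permission directly before it caps non-hematologic events at Grade 3 while leaving hematologic events open upward, a distinction that would otherwise have no purpose. Even if the narrow reading is accepted, Section 12.2.1 still does not grant what footnote a grants, and the oral-intake condition still differs.

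A second argument is that the Medical Monitor is involved on either route. That is correct and it limits the concern: footnote a does not leave continuation to the site alone. It does not remove the conflict, because the monitor would be working from the same two texts.

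Three stronger readings are tempting and are not supported.

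- A reader might infer that Table 9 lets patients restart automatically after a related Grade 4 event, against Section 12.2.1. The rows set thresholds and a dose step; they nowhere waive the consultation.
- A reader might infer that every Grade 4 non-hematologic AE is affected. The conflict over stopping arises only for events judged unrelated. The Section 12.2.4 conditions are separately declared exceptions.
- A reader might infer that safety endpoints are compromised. Protocol Section 7.5.4 names AE reports, physical examination, ECOG status and laboratory evaluations. Dose modifications are descriptive summaries, and SAP Section 5 plans no systematic testing of safety variables.

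**Conclusion.** The point holds for one class of event: Grade 4 non-hematologic AEs judged not related to study treatment. For these, Section 12.2.1 as worded requires suspension, and footnote a to Table 9 allows dosing to be maintained without the oral-intake condition. The disagreement is over whether dosing must stop, not over whether the Medical Monitor is consulted.

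Its reach is blinded and open-label treatment alike. The number of affected events cannot be derived from the documents. The SAP reports that enrollment has concluded, so a correction helps patients still on treatment and the reading of the data already collected.

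The conclusion rests on taking the Grade 4 sentence at its word, as covering all such events whatever their cause. Under the narrower reading the contradiction shrinks to a difference in what the two permissions cover, which still needs correcting. The relation between consultation and restart rows for related Grade 4 events is a secondary clarification. Neither point bears on the primary progression-free survival analysis.

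**What to change.** Reconcile Section 12.2.1 with footnote a of Table 9 so that a single instruction covers unrelated Grade 4 non-hematologic AEs, and have it state whether the oral-intake condition applies. Use the same grade limits in both places. Which instruction to adopt is a clinical decision for the sponsor's clinical team, and this review takes no view on it.

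In the same revision, add a sentence on how the Medical Monitor consultation required by Section 12.2.1 relates to the Table 9 restart rows for related Grade 4 events.

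The cost is a protocol clarification and a letter to sites. No change to the SAP or to any analysis is needed.
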